**SPECIFIC AIMS**

Concisely state the objectives of the study and the hypothesis being tested.

We propose to (1) to target a triplication of *GLDC* by trying to normalize brain glycine levels using D-cycloserine augmentation of usual psychotropic drug treatment, and (2) to characterize the neurobiology of this mutation using neurocognitive and electrophysiology measures and studies of brain structure and function.

**BACKGROUND AND SIGNIFICANCE**

Provide a brief paragraph summarizing prior experience important for understanding the proposed study and procedures.

Multiple rare structural variants of relatively recent evolutionary origin are recognized as important risk factors for schizophrenia (SZ) and other neurodevelopmental disorders [e.g., autism spectrum disorders, mental retardation, epilepsy with odds ratios as high as 7-30 (Sebat et al. 2009; Malhotra et al. 2011; Heinzen et al. 2010; Weiss et al. 2008; McCarthy et al. 2009)]. We have found a *de novo* structural rearrangement on chromosome 9p24.1. In addition to other genes, the duplicated region contains the gene encoding glycine decarboxylase (*GLDC*), which affects brain glycine (Gly) metabolism. Here we focus on the potential contributions of this gene to abnormal glycine homeostasis and N-methyl-D-aspartate receptor (NMDAR) dysfunction in SZ. This mutation is an obvious ‘smoking gun.’ *GLDC* encodes the glycine decarboxylase or glycine cleavage system P-protein, which is involved in degradation of Gly in glia cells. Carriers of the *GLDC* triplication would be expected to have low levels of brain Gly, resulting in NMDA receptor-mediated hypofunction, which has been strongly implicated in the pathophysiology of SZ (Olney & Farmer, 1995; Coyle, 2006; Javitt, 2007). Individuals with mutations that lower brain Gly or alter other aspects of glutamatergic transmission are obvious candidates for Gly augmentation or complementary NMDAR modulatory strategies, which have been used with varying degrees of success [name] et al. 1999; Javitt et al. 2001; Lane et al. 2005; Heresco-[name] et al. 2004; Buchanan et al. 2007). Genetic risk factors, including variants that impact the synthesis and breakdown of Gly, are likely to contribute to this variability.

### **Design of the study:**

Open-label DCS (daily dose of 50 mg) for 8 weeks – Treatment Arm A, followed by four 6-week periods of double-blind DCS or placebo with one week of washout in between. Subjects will be randomized to DCS-placebo-DCS-placebo or to placebo-DCS-placebo-DCS by the McLean Hospital research pharmacist, [name]. These four double-blind exposures (two each for DCS and placebo) will be followed by a 6-week single-blind exposure to DCS (subjects and the person doing the clinical assessments will not know if they are getting DCS or placebo, but Drs. [name], [name], and [name] will know that they are getting DCS). After a one-week washout, this single-blind exposure will be followed by 6 weeks of open-label DCS. The length of each double-blind arm is limited to six weeks to minimize the length of symptom exacerbation experienced by the subjects when they are receiving placebo. The patients’ usual psychotropic drug regimen will not be altered as part of the study, but an attempt will be made to keep those medications unchanged throughout the study if possible. Both the DCS (source: The Chao Center) and the placebo will be dispensed by the McLean Hospital Pharmacy. Throughout the study, subjects will take one vitamin-B complex tablet per day.

[name] will be responsible for medical oversight of the d-cycloserine (DCS) augmentation component of the study. [name] will serve as his back-up. [name] will be responsible for medical oversight of the imaging components of the study.

Briefly describe study procedures. Include any local site restrictions, for example, “Subjects enrolled at Partners will not participate in the pharmacokinetic portion of the study.” Describe study endpoints.

Before beginning the study, subjects will have an EKG and physical exam performed by their personal physician. This will be repeated at week 8 and week 44 at the end of the study. Blood work will be done at the same time and consist of the following tests: comprehensive metabolic profile (CMP), lipid panel, GGT, uric acid, CBC with differential, CRP-hs. Blood will also be drawn for large and small amino acid levels and psychotropic drug levels.

Periodic blood tests and weight checks, clinical ratings (PANSS, Clinical Global Impression scale, Brief Psychiatric Rating Scale, Young Mania Rating Scale, HAM-D), side effect monitoring, movement disorder assessments (AIMS and SAS) and neurocognitive testing (MATRICS) – see schema for details.

The clinical assessment every two weeks includes an evaluation of suicidality (HAMS and C-SSRS). In addition, there is an at least once-weekly call with [name] to monitor changes in symptoms. Should any suicidal ideation emerge, [name] and [name] would review the symptoms and their acuteness with [name] (or [name]). [name] (or [name]) would talk with the subject. We would then have a conference call involving [name], [name], and [name] ([name] should [name] not be available) to discuss the best disposition: determining whether a subject need to be hospitalized, whether the subject should be discontinued from the study; whether emergency services (911) should be notified. We would confer with the subject's psychiatrist and notify the internist. We would discuss with the subject what we feel is the best plan going forward and facilitate whatever disposition seems best. The subject's family would be informed (with written permission from the subject obtained in the informed consent) to help ensure prompt compliance with the disposition.

The imaging procedures have been used extensively at McLean without complications. Both subjects will be carefully screened again for the safety of the imaging procedures. Both subjects have had multiple brain scans at McLean in the recent past. Baseline imaging data collected in the glycine study will serve as baseline data in this study.

The PI has talked with all of the people involved in the study (Drs. [name], [name], [name], [name], [name]; [name], [name]) to ascertain that they are all in agreement that the proposed plan for medical and/or psychiatric monitoring for the patients while they are taking a novel compound is adequate. [name] is the primary medical back-up; [name] is back-up

if [name] is unavailable. [name] is an unpaid consult with expertise in using DCS. Drs. [name] and [name] are the treating psychiatrists of the subjects. [name] performs all clinical assessments. [name] is the research pharmacist.

Describe explicitly the methods for ensuring the safety of subjects. Provide objective criteria for removing a subject from the study, for example, objective criteria for worsening disease/lack of improvement and/or unacceptable adverse events. The inclusion of objective drop criteria is especially important in studies designed with placebo control groups.

#### **FORESEEABLE RISKS AND DISCOMFORTS**

Provide a brief description of any foreseeable risks and discomforts to subjects. Include those related to drugs/devices/procedures being studied and/or administered/Performed solely for research purposes. In addition, include psychosocial risks, and risks related to privacy and confidentiality. When applicable, describe risks to a developing fetus or nursing infant.

The procedures described above pose no serious physical risk to subjects and no psychological, social, or legal risks are anticipated.

The scans involve use of a standard clinical MRI scanner (3T) as well as a high field (4T) MRI scanner. The 4T scanner is not used for routine clinical studies in children or adults, but the FDA has determined (July 14, 2003) that scanners with magnetic field strengths of less than 8 Tesla do not represent a significant risk to adults, children, or infants older than 1 month. Most people experience no ill effects from 3T or 4 T scans, but some do report claustrophobia, dizziness, mild nausea, headaches, a metallic taste in their mouth, back tingling, double vision,

or sensation of flashing lights. These symptoms, if present, disappear shortly after leaving the scanner. During the scan, the examiner can see and hear the subjects and will ask them to report any problems so the scan can be stopped if necessary. A magnetic resonance scan may be uncomfortable due to claustrophobia, lying still for an hour, or loud sounds. Subjects who express serious concern about these will not be included. The scan will be stopped if the subject expresses discomfort. Total time in the scanner for the structural scan and 2 MRS scans at McLean is 150 minutes, with breaks occurring between scans (structural: 15 minutes; MEGAPRESS: 60 minutes; J-PRESS: 75 minutes). The DCS uptake scan requires multiple scans over a two hour period in the scanner. Subjects will be allowed to leave the scanner between scans and can be re-positioned for the next scan, as described in the application. Both subjects have successfully completed imaging procedures.

DCS Augmentation Clinical Trial: Pharmaceutical grade DCS (The Chao Center) will be used. The dose will be 50 mg/d, which is well within the range of doses that were well tolerated in previous patient studies ([name] et al. 1999a, b, 2005, 2008; Heresco-[name] et al. 1998, 2002). No adverse effects on kidney, liver, hematology or blood chemistry values have been reported. The subjects will be monitored closely by the research team and by their own psychiatrists. Blood chemistries, including liver/kidney function tests, will be monitored at baseline and monthly during the open-label DCS treatment arm as well as every 6 weeks after that. As mentioned above, at the low dose of DCS that we plan to use, the only reported psychiatric side effect was a modest and time-limited worsening of negative symptoms in a small minority of patients who were taking clozapine; this effect may be related to having a high DCS plasma level ([name] et al. 1996, 1999a, b). Interestingly, this mild worsening was not “particularly distressing to patients or clinicians” ([name] et al. 1999a). Subjects will also take one vitamin B-complex tablet/day to ensure that they do not develop B12 and folate deficiency. These are unlikely at the low dose of DCS (50 mg) that will be used.

Periodic blood samples involve the slight discomfort of a needle stick and the small risk of a bruise. Every attempt is made to have the subject feel comfortable and at ease with the environment and the staff. Subjects are debriefed at the end of the day by the study coordinator at which time they can ask questions and express their reactions to the study. Subjects who wish to discontinue the study may withdraw at any time.

Risks to privacy and confidentiality are minimal. All subjects are assigned a random 4-digit ID number, which is used to code all material.

## **EXPECTED BENEFITS**

Describe both the expected benefits to individual subjects participating in the research and the importance of the knowledge that may reasonably be expected to result from the study. Provide a brief, realistic summary of potential benefits to subjects, for example, “It is hoped that the treatment will result in a partial reduction in tumor size in at least 25% of the enrolled subjects.” Indicate how the results of the study will benefit future patients with the disease/condition being studied and/or society, e.g., through increased knowledge of human physiology or behavior, improved safety, or technological advances.

The general goal of this study is to clarify the neurobiology of a mutation in glycine metabolism and to determine whether carriers of this mutation may preferentially benefit from DCS augmentation of their medication regimen. Although subjects receive no immediate benefit from the brain imaging procedures beyond contributing to important research, the potential scientific yield could have a major impact on identifying causal mechanisms in psychotic disorders. If the DCS augmentation is beneficial, these two subjects may experience a significant reduction in psychotic symptoms and improvement in neurocognition, which may also help other subjects

with mutations impacting the glycine metabolic pathway. Since both subjects responded well to glycine, which is a cumbersome to use and an unrealistic long-term treatment, DCS, which is available in a once daily pill would be a helpful long-term clinical adjunct if it is shown to be effective.

## EQUITABLE SELECTION OF SUBJECTS

The risks and benefits of the research must be fairly distributed among the populations that stand to benefit from it. No group of persons, for example, men, women, pregnant women, children, and minorities, should be categorically excluded from the research without a good scientific or ethical reason to do so. Please provide the basis for concluding that the study population is representative of the population that stands to potentially benefit from this research.

The only scientific and ethical justification for including subjects in this study is if their participation can help to clarify the neurobiology of a mutation in glycine metabolism and if they might benefit from DCS augmentation. All other subjects are excluded. Therefore, the only eligible participants at the present time are two carriers of this specific genetic mutation who also have a diagnosis of a psychotic disorder and have participated in the Neurobiology of a Mutation in Glycine Metabolism in Psychotic Disorders (2012P001597) protocol. To our knowledge, this is a private mutation although different mutations in the same gene have been reported in other individuals with psychotic disorders and with autism spectrum disorders. These individuals may be potentially eligible for a similar augmentation intervention.

When people who do not speak English are excluded from participation in the research, provide the scientific rationale for doing so. Individuals who do not speak English should not be denied participation in research simply because it is inconvenient to translate the consent form in different languages and to have an interpreter present.

N/A

For guidance, refer to the following Partners policy:

Obtaining and Documenting Informed Consent of Subjects who do not Speak English

[https://partnershealthcare-public.sharepoint.com/ClinicalResearch/Non-English\\_Speaking\\_Subjects.1.10.pdf](https://partnershealthcare-public.sharepoint.com/ClinicalResearch/Non-English_Speaking_Subjects.1.10.pdf)

## RECRUITMENT PROCEDURES

Explain in detail the specific methodology that will be used to recruit subjects. Specifically address how, when, where and by whom subjects will be identified and approached about participation. Include any specific recruitment methods used to enhance recruitment of women and minorities.

The subjects will be selected on the basis of having a triplication of the GLDC gene, a mutation involving an abnormality in glycine metabolism that may be implicated in psychotic disorders, a psychotic disorder, and having participated in the Neurobiology of a Mutation in Glycine Metabolism in Psychotic Disorders (2012P001597) protocol. Prior to beginning the study, the PI will call the subjects and review all of the procedures and time frames. The subjects will be flown to Boston for the McLean procedures and to Minneapolis for the UMN procedures. Other procedures will be carried out in the subjects' city of residence. The procedures will be scheduled well in advance to minimize inconvenience to the subjects and to optimize successful data collection at McLean.

Provide details of remuneration, when applicable. Even when subjects may derive medical benefit from participation, it is often the case that extra hospital visits, meals at the hospital, parking fees or other inconveniences will result in additional out-of-pocket expenses related to study participation. Investigators may wish to consider providing reimbursement for such expenses when funding is available

Each subject will be paid \$1,000 for completing the open-label DCS study and \$1,000 for completing the entire double-blind DCS-placebo study. They will each be paid \$200 for the UMN procedures. The imaging, electrophysiology procedures will involve at least 1 week away from work other responsibilities. All expenses incurred as part of participating (e.g., travel, hotel, local transportation, and meal costs) will be paid for by the grant supporting this study. Subjects will be paid a pro-rated amount if unable to complete all procedures based on the proportion of the study that was completed. For example, if a subject completes 80% of the procedures, that subject would be paid \$800. Any additional expenses related to participation, such as gas or taxis, up to \$500.00 in year 1 and up to \$300 in year 2, will be reimbursed based on submitted receipts.

For guidance, refer to the following Partners policies:

Recruitment of Research Subjects

[https://partnershealthcare-public.sharepoint.com/ClinicalResearch/Recruitment Of Research Subjects.pdf](https://partnershealthcare-public.sharepoint.com/ClinicalResearch/Recruitment%20Of%20Research%20Subjects.pdf)

Guidelines for Advertisements for Recruiting Subjects

[https://partnershealthcare-public.sharepoint.com/ClinicalResearch/Guidelines For Advertisements.1.11.pdf](https://partnershealthcare-public.sharepoint.com/ClinicalResearch/Guidelines%20For%20Advertisements.1.11.pdf)

Remuneration for Research Subjects

[https://partnershealthcare-public.sharepoint.com/ClinicalResearch/Remuneration for Research Subjects.pdf](https://partnershealthcare-public.sharepoint.com/ClinicalResearch/Remuneration%20for%20Research%20Subjects.pdf)

## CONSENT PROCEDURES

Explain in detail how, when, where, and by whom consent is obtained, and the timing of consent (i.e., how long subjects will be given to consider participation). For most studies involving more than minimal risk and all studies involving investigational drugs/devices, a licensed physician investigator must obtain informed consent. When subjects are to be enrolled from among the investigators' own patients, describe how the potential for coercion will be avoided.

The PI and [name], a licensed physician who provides medical back-up for the study, will obtain written informed consent after reviewing the purposes of the study, detailing the procedures and explaining the informed consent documents. The subjects will have several weeks to consider participation. The subject will be given an opportunity to ask questions after which written informed consent is obtained. Competence to give informed consent will be determined by the PI based on the subject's understanding of the purpose of the study and procedures, what they involve, how long they take, and risk and benefits. The subject receives a copy of the Informed Consent for his/her own files.

NOTE: When subjects are unable to give consent due to age (minors) or impaired decision-making capacity, complete the forms for Research Involving Children as

Subjects of Research and/or Research Involving Individuals with Impaired Decision-making Capacity, available on the New Submissions page on the PHRC website:  
<https://partnershealthcare.sharepoint.com/sites/phrmApply/aieipa/irb>

For guidance, refer to the following Partners policy:

Informed Consent of Research Subjects:

[https://partnershealthcare-public.sharepoint.com/ClinicalResearch/Informed Consent of Research Subjects.pdf](https://partnershealthcare-public.sharepoint.com/ClinicalResearch/Informed%20Consent%20of%20Research%20Subjects.pdf)

## DATA AND SAFETY MONITORING

Describe the plan for monitoring the data to ensure the safety of subjects. The plan should include a brief description of (1) the safety and/or efficacy data that will be reviewed; (2) the planned frequency of review; and (3) who will be responsible for this review and for determining whether the research should be altered or stopped. Include a brief description of any stopping rules for the study, when appropriate. Depending upon the risk, size and complexity of the study, the investigator, an expert group, an independent Data and Safety Monitoring Board (DSMB) or others might be assigned primary responsibility for this monitoring activity.

NOTE: Regardless of data and safety monitoring plans by the sponsor or others, the principal investigator is ultimately responsible for protecting the rights, safety, and welfare of subjects under his/her care.

The scientific integrity of the study and protection of participant safety will be monitored by the investigators using an Adverse Event Tracking Log, including the detection and reporting of adverse events. The safety data include all imaging procedures, the neurocognitive function battery, as well as the double-blind placebo-controlled and open-label DCS augmentation trials. Efficacy data includes all DCS-related procedures.

All adverse events will be promptly reported to the Partners Human Research Committee (PHRC) and NIMH as appropriate. At a minimum, the investigators will review all adverse events at the end of each treatment arm, but more often if needed. Unanticipated problems involving risks to subjects or others including adverse events will be reported to the PHRC in accordance with PHRC unanticipated problems reporting guidelines.

The research will be altered or stopped if subjects have adverse reactions to any of the procedures (e.g., claustrophobia in the scanners) or significant side effects to DCS. The dose of DCS used in the augmentation trials (50 mg/d) is well tolerated and is a standard dose used in clinical trials. [name], a consultant on this project, has a great deal of experience in using DCS to augment the therapeutic effects of antipsychotic medication. [name] will be available to discuss ongoing clinical states, side effects, and to address any relevant management issues. At least once every week, the subjects will receive a phone call from [name] to discuss how they are feeling and to review side effects. At the end of the first week of DCS, the subjects will also be called by a study physician ([name]) to assess how they are reacting to the DCS or placebo. Both subjects' psychiatrists will also be monitoring their clinical states and side effects throughout the study. Subjects will be told that if they experience any side effects, they must report them to [name] or any of the other co-investigators immediately (phone and page numbers through the McLean Hospital operator will be provided).

Partners Collaborative Media (PCM) will provide oversight (for a fee) to ensure that the clinical assessments taking place every two weeks using skype-like video conferencing are secure. Specific web cameras recommended by PCM will be used by McLean staff and by the subjects. All calls will be initiated from McLean using a Partners computer. This computer will have the Cisco program, "movi" [mobile video], installed. PCM will create generic credentials for the subjects such that they will not be using their own actual skype credentials. Thus, if the skype material is stolen, it cannot be linked to the subjects themselves. A McLean clinician will call the subjects by clicking on customized phone numbers and allow the McLean caller to lock the virtual meeting room.

A technical statement about how the secure connection will be implemented has been uploaded.

Describe the plan to be followed by the Principal Investigator/study staff for review of adverse events experienced by subjects under his/her care, and when applicable, for review of sponsor safety reports and DSMB reports. Describe the plan for reporting adverse events to the sponsor and the Partners' IRB and, when applicable, for submitting sponsor safety reports and DSMB reports to the Partners' IRBs. When the investigator is also the sponsor of the IND/IDE, include the plan for reporting of adverse events to the FDA and, when applicable, to investigators at other sites.

NOTE: In addition to the adverse event reporting requirements of the sponsor, the principal investigator must follow the Partners Human Research Committee guidelines for Adverse Event Reporting

Subjects will be discontinued from the study if the BPRS shows a 25% worsening or severity of specific symptoms changes by two additional points (compared with baseline). Any adverse events will be immediately reported to the IRB.

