After the discontinuation period is completed, the subjects will receive open-label DCS (50 mg/d) for 8 weeks. Subjects will be formally evaluated on all of the clinical measures (see below and schema) every two weeks but will be in weekly phone contact with the PI throughout. Although we do not anticipate that DCS will cause a worsening of their symptoms, we cannot rule out this possibility in advance. If the BPRS shows an additional 25% worsening or severity of specific symptoms changes by two additional points (compared to their new baseline), that subject will be discontinued. [name] will review the clinical data before a subject is discontinued. . Subjects who complete the open label DCS trial will be randomized to DCS or placebo for 6-week periods in a double-blind design. The McLean Hospital research pharmacist, [name], will determine the randomization and will not be blind to drug or placebo condition, but the subjects and all other study staff will be. There will be a total of four 6-week double-blind exposures to DCS or placebo, each followed by one week of washout. A one-week washout is more than sufficient for both a behavioral and biochemical washout (half-life of DCS is 10 hours, so technically, two days should be sufficient). The two possible randomization schemas are: DCS-placebo-DCS-placebo or placebo-DCS-placebo-DCS, to be determined by the research pharmacist. We are limiting the length of each double-blind arm to six weeks to minimize the length of symptom exacerbation experienced by the subjects when they are receiving placebo. These four double-blind exposures (two each for DCS and placebo) will be followed by a 6-week single-blind exposure to DCS (subjects and the person doing the clinical assessments will not know if they are getting DCS or placebo, but Drs. [name], [name], and [name] will know that they are getting DCS). After a one-week washout, this single-blind exposure will

be followed by 6 weeks of open-label DCS. Subjects will be aware of the design and thus will know that if they experience a worsening of symptoms in any clinical arm, it will be time-limited.

II. Specific Aims

a. Objectives/hypotheses

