The subjects will also be given emergency contact numbers for Drs. [name], [name], [name], and [name]. The subjects will also be told to go the nearest emergency room if they experience any acute side effects (e.g., vomiting, diarrhea). [name], a consultant on this project, has a great deal of experience in using DCS to augment the therapeutic effects of antipsychotic medication and will be available to advise the study team about any needed changes (i.e., dose reduction, discontinuation) based on side effects or changes in clinical state. Decisions about how best to proceed will be made in consultation among Drs. [name], [name], ([name] if [name] is not available), [name], and the McLean pharmacist. Based on [name] extensive experience

using this dose of DCS, it is very unlikely that it will be necessary to discontinue the trial altogether. Should there be changes in any arm of the study, such as temporary discontinuation or extending the time period, the IRB will be notified. If subjects develop side effects that make them too uncomfortable or that make it medically necessary to discontinue the study, the study will be stopped. This level of oversight for subjects who are not local seems reasonable for monitoring subjects taking a compound that has been safely used as an augmentation strategy. The same procedures were used in the initial glycine augmentation study and the current extended glycine trial and have worked effectively.

The PI has talked all of the people involved in the study (Drs. [name], [name], [name], [name], [name], and [name]; [name]) about the adequacy of the plan to provide medical and/or psychiatric monitoring of these patients while they are taking a novel compound; they have agreed that the proposed plan is acceptable. [name] is the psychiatrist for one of the subjects and [name] is the psychiatrist for the other. Blood work results are faxed to them and they are kept apprised of any notable developments (e., beginning and end of any phase of the study, worsening of clinical state, improvement in clinical state). They, in turn, contact the PI if they become concerned about changes in clinical state or side effects.

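### The Protocol's symptom-worsening rule ends study participation in any phase, the SAP's version leaves its scope open, and neither says what a crossing ends in the blinded arms

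*Protocol*

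**What the plan says.** Four places bear on this.

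- Protocol, Data and Safety Monitoring: "Subjects will be discontinued from the study if the BPRS shows a 25% worsening or severity of specific symptoms changes by two additional points". The comparison is with a baseline that the section does not define, and no arm or phase is named.
- SAP, design description at the end of Section I. The open-label text first allows for drug-induced worsening: "Although we do not anticipate that DCS will cause a worsening of their symptoms, we cannot rule out this possibility in advance". The rule follows: "If the BPRS shows an additional 25% worsening or severity of specific symptoms changes by two additional points". Its yardstick is the level reached after the glycine washout, and discontinuation follows with neither arm nor study named as what ends. A study clinician reviews the data before anyone is discontinued. Only subjects who complete the open-label phase are randomized. The paragraph ends by saying subjects will understand that "if they experience a worsening of symptoms in any clinical arm, it will be time-limited".
- SAP Section IX: "Should there be changes in any arm of the study, such as temporary discontinuation or extending the time period, the IRB will be notified".
- Protocol, Design of the study: the blinded arms are "limited to six weeks to minimize the length of symptom exacerbation experienced by the subjects when they are receiving placebo". The SAP's design description gives the same reason.

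SAP item 3 (Glycine Washout) sets the new clinical baseline. It is reached after glycine is stopped, at a 25% BPRS worsening and/or a CGI severity change of 1–2 points, and is taken as week 0.

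**The concern.** The design expects symptoms to worsen on placebo, and the discontinuation rule runs on the BPRS, which is also one of the clinical ratings used to judge benefit. If the rule applies in Arms B–E and ends the study for that subject, exit depends on the outcome and is more likely on placebo. The more benefit a subject loses on placebo, the less blinded data remain. Only two carriers are eligible (Protocol, Equitable Selection of Subjects), so a lost subject cannot be replaced.

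The documents leave the scope unsettled. Two staff members faced with the same rating in a blinded arm could act differently and each point to the text. SAP Section VI plans to relate change scores on DCS and placebo, but does not say how an arm cut short would count. No available section says whether ratings continue after a subject is discontinued.

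**Working it through.** **1. Schedule.** The inputs are the arm and washout lengths in SAP items 4–8.

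8 + 1 + 4 × (6 + 1) + 6 + 1 + 6 = 50 weeks, which reproduces the SAP's stated 50 weeks. The blinded arms fall at weeks 10–15 (B), 17–22 (C), 24–29 (D) and 31–36 (E). Ratings in Arm B are at weeks 11, 13 and 15, so the corresponding times in Arm C are weeks 18, 20 and 22.

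**2. What remains if a subject leaves in the first placebo arm** (Protocol wording applied literally).

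- Placebo first: exit at week 11, 13 or 15. No blinded DCS arm has been given, so 0 of 2 DCS–placebo pairs exist.
- DCS first: exit at week 18, 20 or 22. One full blinded DCS arm and at most one placebo arm exist, so at most 1 of 2 pairs, truncated unless exit is at the last rating.

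**3. Chance that neither subject has a blinded contrast, if both cross on first placebo.** The documents say the research pharmacist determines the sequence but give no allocation method, so this is a range over assumptions:

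- independent 1:1 draws: 0.5 × 0.5 = 25%;
- one subject per sequence: 0%;
- both share one randomly drawn sequence: 50%.

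The chance that at least one subject has none is 1 − 0.5² = 75%, 100% and 50% respectively.

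**4. Would the expected worsening reach the BPRS threshold?** Neither document gives its size. As an illustration, set the on-glycine BPRS level to 1.00, assume week 0 was set at exactly 25% above it (1.25), and suppose placebo returns the subject to 1.25.

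- Against the on-glycine level: 1.25 / 1.00 − 1 = +25%, threshold met.
- Against the SAP's new baseline: 1.25 / 1.25 − 1 = 0%, not met.
- Against the end of open-label DCS, if DCS had reversed half the washout worsening (level 1.125): 1.25 / 1.125 − 1 = +11%, not met. If it had reversed all of it (level 1.00): +25%, met.

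An additional 25% on top of week 0 would be 1.25 × 1.25 = 1.5625, or +56% over the on-glycine level. The two versions of the rule can therefore be far apart. The two-point symptom limb cannot be worked out from the documents.

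**5. Timing.** SAP item 3 expects worsening within about one month of stopping glycine. If stopping DCS behaved alike (an assumption), four weeks after the last dose is the end of week 12 for placebo first (8 + 4; next rating week 13) and the end of week 19 for DCS first (15 + 4; next rating week 20). Both fall inside the 6-week arm.

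**The case against.** Three stronger readings are tempting, and the documents support none of them.

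- *A reader might infer three conflicting rules: study exit in the Protocol, open-label exit only in the SAP, and a pause or wait in later arms.* The SAP's sentence does not say what is ended; its open-label scope is read from where it sits. Because non-completers are not randomized, discontinuation there also bars the blinded phase. The remark about time-limited worsening describes what subjects will know about the design and is compatible with an exit rule. Section IX mentions no BPRS threshold.
- *A reader might infer that the predicted placebo worsening would remove a subject before any blinded contrast exists.* No size is predicted, the result turns on the baseline, and loss of every contrast applies to only one of the two sequences. The Protocol's wording, "severity of specific symptoms changes by two additional points (compared with baseline", keeps the word additional, so it may simply be a shortened form of the SAP rule with the same baseline.
- *A reader might infer that the treatment difference will be biased toward zero.* That would follow if arms cut short by worsening on placebo were dropped, but SAP Section VI proposes no completed-arms analysis. It describes magnitude of change and correlations in two people and disclaims being a population study. Ratings up to exit, including the triggering one, would already be in hand.

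It is also fair that the SAP's rule is not automatic, since the data are reviewed first. Parts of both documents and the schema are not available and may define the baseline or scope.

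These points limit the consequence. The Protocol's unrestricted study exit, the SAP's unspecified one, and silence on Arms B–E remain.

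**Conclusion.** The point holds as an unreconciled scope and an undefined reference level for a rule that acts on an outcome scale. The potential loss is one or both of a subject's two blinded DCS–placebo pairs, depending on sequence, with no replacement. It arises only if the Protocol wording is applied in the blinded arms and a subject crosses the threshold on first placebo. The probability of crossing cannot be computed from the documents. The 0% to 50% range for losing the blinded contrast in both subjects is conditional on both crossing and reflects only the unstated allocation method. The baseline illustration assumes that week 0 was reached at exactly 25% on the BPRS, although CGI severity alone can also define it. The matter is worth settling before the blinded arms begin; it does not show that the trial will fail.

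**What to change.** Reconcile the Protocol's Data and Safety Monitoring rule, the SAP's design description and SAP Section IX so that they state one scope (arm, study drug or study) and one reference baseline for a threshold crossing in Arms B–E. The clinical rule is for the sponsor to choose. If removed pages already settle either matter, a cross-reference is enough.

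Then, for the data:

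- distinguish stopping study drug from leaving the study, and continue the already scheduled remote ratings for subjects who agree; blood draws after exit need not be required;
- state in SAP Section VI that ratings up to exit, including the triggering one, enter that arm's DCS–placebo comparison, so that the arm is not dropped;
- report the number of arms ended by the rule, by treatment.

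The cost is wording in both documents and a matching consent term. The small downside is that a subject who has stopped study drug, possibly while unwell, is asked to keep attending remote ratings.
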